**Part A:**

Approximately 70 subjects who are currently not being treated for their CHB infection will be randomized in a 3:1:3 ratio to receive one of the following treatments:

- Treatment Arm 1: JNJ-56136379 (N=30) (open-label)

After full recruitment, this treatment arm was discontinued early per Protocol Amendment 4. All subjects were to stop further dosing with JNJ-56136379 75 mg, start treatment with NA, and enter the post-treatment follow-up phase (Schedule 1).

- Treatment Arm 2: Placebo + NA (ETV or TDF) (N=10)
- Treatment Arm 3: JNJ-56136379 + NA (ETV or TDF) (N=30)

At the same time, approximately 40 subjects who are virologically suppressed by current NA treatment will be randomized in a 1:3 ratio to receive one of the following treatments:

- Treatment Arm 4: Placebo + NA (ETV or TDF) (N=10)
- Treatment Arm 5: JNJ-56136379 + NA (ETV or TDF) (N=30)

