For subjects who continue study drugs until Week 48, treatment completion criteria (Section 6.3) are included to explore the possibility of finite treatment. The treatment completion criteria which take ALT, HBV DNA, HBeAg and HBsAg levels into consideration, have been selected to ensure that only subjects with a chance of sustained off-treatment response are allowed to complete all HBV treatment. Multiple studies have shown that patients with low HBsAg levels and/or with on-treatment reduction in HBsAg have an improved likelihood of off-treatment response. Thus, inclusion of the HBsAg parameters in the treatment completion criteria should ensure that patients have experienced a treatment response in terms of HBsAg reduction and reached a favorable HBsAg level. From a safety perspective, data from the 9 months toxicity data in dogs support a treatment duration of 48 weeks in humans. (Section 1.1).

Two doses of JNJ-56136379 will be evaluated in this Phase 2a study. Based on all available data from the Phase 1 study 56136379HPB1001 in treatment-naïve CHB-infected subjects treated for 28 days, 75 mg was selected as the JNJ-56136379 low dose. The mean HBV DNA reductions observed with 4 weeks of 75 mg monotherapy ( $2.89 \log_{10}$  IU/mL) were similar to the HBV DNA declines observed with ETV and TDF suggesting similar potency to NAs at therapeutic doses with the low 75 mg dose.

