*Status changes from baseline at week 24 and at week 48 (only subjects with treatment extension)* for HBsAg, HBeAg, anti-HBs and anti-HBe status. Only the qualitative result will be considered. Use the selected time point for the week 24 or 48 visit as described in 2.3. The following categories were defined. The categories can be extended when missing values are present. A borderline result will be mapped as negative.

- Positive to Positive
- Negative to Negative
- Negative to Positive
- Positive to Negative

Maximum decrease from baseline is defined as the minimum value for change of baseline for the viral activity parameters HBeAg, HBsAg, HBVRNA, HBVDNA and HBcrAg)

*Biochemical response* or alanine aminotransferase (ALT) normalization from baseline per post-baseline time point is defined for subjects with elevated ALT (ALT>ULN) at baseline as:

- 0 (No) = ALT>ULN
- 1 (Yes) = ALT $\leq$ ULN

*On-treatment failure during week 24 period is defined as:*

- Subject who has at week 4 HBVDNA < 1log10 IU/mL decline from baseline and confirmed by retesting at week 8 visit (apply only for the naïve treatment population)
- Or for subject who experienced viral breakthrough as defined above

*On-treatment failure during week 48 period is defined as:*

- Subject whom after completed week 24 treatment and still on JNJ-56136379 experienced viral breakthrough as defined above

---

- Subject who did not meet the treatment extension criteria at week 24 as defined in the protocol (this should be derived using the criteria below)
  - Completed 24 weeks of treatment
  - HBVDNA levels < 200 IU/mL at week 20
  - No safety concerns during the initial 24 weeks of treatment
- Subject who did not meet the week 40/44 treatment completion criteria as defined in the protocol (this should be derived using the criteria below)
  - Completed 48 weeks of treatment
  - At week 40 and confirmed at week 44
    - Normal ALT levels or elevated ALT levels by investigator opinion
    - HBV DNA <LLOQ
    - HBeAg negative
    - HBsAg < 500 IU/mL
    - $\geq 1$  log10 IU/mL decline in HBsAg from baseline

*Post-treatment failure during follow-up with NA treatment is defined as:*

Subject who completed study treatment at week 24 and did not met the treatment extension criteria or subject who did not met treatment completion criteria at week 48 as defined above or subjects who discontinued study treatment earlier and experienced viral breakthrough as defined above (NA treatment)

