### 7.3. Parameters to Analyze

At specified time points and for each list specified in the section below, the following parameters will be analyzed:

- Number (%) of subjects with a genetic variation at a specific position.
- Number (%) of subjects with a specific genetic variation.
- Number (%) of subjects with genetic variations on amino acid level (at positions of interest) in the HBV core protein, HBV core protein positions (47, 28, 15), HBV core protein positions in HBV genotype (A, B, C, D, E, F, G, H and I), polymerase region, precore mutation and basal core promotor region (nucleotide level for PC and BCP) mutation ( Will be presented in separate report not in the CSR)
- Number (%) of subjects with substitutions on amino acid level (at positions of interest) in the HBV core protein, HBV core protein positions of interest (47, 28, 15), HBV core protein positions in HBV genotype (A, B, C, D, E, F, G, H and I), polymerase region, precore mutation and basal core promotor region (nucleotide level for PC and BCP) mutation
- Number (%) of subjects with treatment-emergent substitutions on amino acid level at end of treatment, at time of failure (in subjects with treatment failure as defined in section 5.3.1), at time of viral breakthrough (in subjects with viral breakthrough as defined in section 5.3.1), t time of viral relapse (in subjects with viral relapse as defined in section 5.3.1) by substitution profile in the HBV core protein position of interest (28, 15)
- Number (%) of subjects with treatment-enriched substitutions on amino acid level at end of treatment, at time of failure (in subjects with treatment failure as defined in section 5.3.1), at time of viral breakthrough (in subjects with viral breakthrough as defined in section 5.3.1), t time of viral relapse (in subjects with viral relapse as defined in section 5.3.1) by substitution profile in the HBV core protein position of interest (28, 15)

The focus will be on genetic variations at a time point, emerging genetic variations and reversion to wild type or baseline state.

Sequence variations will be analyzed and reported on both the nucleotide level (for example for changes in the basal core promotor and precore region) as well as on amino

---

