acid (aa) level. In the sequence analysis, sequences will be mapped to the respective genotype specific reference sequences after which nt changes and aa substitutions will be annotated compared to the respective genotype specific reference (see Table in section 7.2). In addition, the X02763 (HBV genotype A), which is the master reference sequence of the HBV db, will be used as universal reference sequence.

All NGS data will be collected using a nt and aa read frequency cut-off of  $\geq 0.01$ . For the analysis of baseline nt changes and/or aa substitutions in terms of prevalence and impact on treatment outcome, a read frequency cut-off of  $\geq 0.15$  will be used. The analysis of treatment-emergent nt changes or aa substitutions will consider nt changes or aa substitutions absent at baseline ( $< 0.01$  read frequency) but present at a read frequency of  $\geq 0.15$  at later time points. Virology analyses based on NGS data will also evaluate treatment-enriched nt changes and aa substitutions, defined as present at baseline with a read frequency  $\geq 0.01$  but  $< 0.15$  and with an increase in read frequency of at least 0.15 post-baseline. A minimum increase in read frequency of 0.15 compared to baseline excludes small, potentially technical variations in the read frequency of minority nt changes and aa substitutions which are not expected to have clinical relevance. In addition, for subjects with treatment failure nt changes and aa substitutions detected with a read frequency  $\geq 0.01$  at baseline, at time of failure and at end of study will be described in a listing. The persistence of treatment-emergent nt changes and aa substitutions will be evaluated using a cut-off of  $\geq 0.15$  and  $\geq 0.01$ .

The applicability of the sequencing approach described here (eg, the 0.01 sensitivity limit) will be assessed during the development program and might be adapted if needed.

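### The SAP's Week 48 on-treatment failure flag includes subjects who merely do not qualify to stop all therapy or who were stopped early, which blurs the resistance tables for treatment failure

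*SAP*

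**What the plan says.** The parameter definitions under SAP Section 5.3 (misnumbered 5.2.1; SAP Section 7 cites them as 5.3.1) give three bullets for on-treatment failure during the Week 48 period, with no and/or between them:

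- The first is late breakthrough on the investigational drug: "Subject whom after completed week 24 treatment and still on JNJ-56136379 experienced viral breakthrough as defined above".
- The second is ineligibility for the extension: "Subject who did not meet the treatment extension criteria at week 24 as defined in the protocol".
- The third is ineligibility to stop all therapy: "Subject who did not meet the week 40/44 treatment completion criteria as defined in the protocol".

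The second bullet's components are 24 weeks completed, HBV DNA below 200 IU/mL at Week 20, and no safety concern. The third bullet's first component is "Completed 48 weeks of treatment". The rest apply at Week 40 with confirmation at Week 44: an ALT condition, HBV DNA below LLOQ, HBeAg negative, HBsAg below 500 IU/mL, and an HBsAg fall of at least 1 log10. Neither bullet is restricted by arm or to extension participants.

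The protocol's Study Design Rationale says the completion criteria "have been selected to ensure that only subjects with a chance of sustained off-treatment response are allowed to complete all HBV treatment". Protocol Section 6.3 applies them to that decision, and Section 2.1 makes meeting them an extension-phase endpoint of its own. On Arm 1, Protocol Section 3.1 states: "All subjects were to stop further dosing with JNJ-56136379 75 mg, start treatment with NA".

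SAP Section 7.3 uses the failure definitions to tabulate substitutions "at time of failure (in subjects with treatment failure as defined in section 5.3.1") and to prepare a listing "for subjects with treatment failure nt changes and aa substitutions detected with a read frequency" of at least 0.01. The other-analysis text in SAP Section 7.5 repeats the listing.

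**The concern.** A rule for who may safely stop everything is a demanding target. Not reaching it is different from failing on treatment: under Protocol Section 6.3 such a subject simply continues or starts NA. The SAP's neighbouring definitions all rest on a virologic event. Week 24 failure is Week 4/8 non-response or breakthrough, and the two post-treatment failures need breakthrough or relapse. In the Week 48 rule, missing the criteria is itself the event.

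Protocol Section 11.3.2 wants resistance changes described in subjects not responding to treatment. If that group also holds suppressed subjects, subjects stopped by sponsor decision and subjects stopped for safety, its substitution counts no longer describe failure linked to resistance. This trial's 75 mg monotherapy arm was closed because of breakthrough, so that description matters.

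**Working it through.** **How the bullets combine.** The first needs a subject still on JNJ-56136379 after Week 24; the second needs one who did not qualify to continue. Requiring all three would leave the category empty, so each is sufficient alone. The first cannot apply to placebo+NA, so controls enter the Week 48 flag only through the second and third.

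**No stated figure to reproduce.** Neither document gives an expected failure rate. I therefore bound it with one necessary condition, the HBsAg fall of at least 1 log10:

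P(pass) ≤ Φ((−1 − mean)/SD), and failure ≥ 1 − P(pass).

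**Inputs (Protocol Section 11.2, Table 7, Week 24 change).** Controls: −0.35 ± 0.6 in untreated HBeAg-positive subjects and −0.05 ± 0.4 in the other three subgroups. JNJ-56136379+NA: −1.35 ± 2.16 and −1.05 ± 2.16 respectively. Cells per part, in the order untreated HBeAg-positive, untreated HBeAg-negative, suppressed HBeAg-positive, suppressed HBeAg-negative: controls 4/6/3/7, JNJ-56136379+NA 12/18/9/21. Week 24 stands in for Weeks 40/44 (assumption).

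**Controls.**
- Three subgroups: Φ(−0.95/0.4) = 0.0088, so failure ≥ 99.1%.
- Untreated HBeAg-positive: Φ(−0.65/0.6) = 0.139, so failure ≥ 86.1%.
- Overall: (4 × 0.861 + 16 × 0.991)/20 = 19.3/20, or 96.5%.
- If no HBeAg-positive control loses HBeAg: (7 + 13 × 0.991)/20 = 99.4%.
- If mean declines double by Weeks 40/44: Φ(−0.9/0.4) = 0.012 and Φ(−0.3/0.6) = 0.31, giving (4 × 0.69 + 16 × 0.988)/20 = about 93%.

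**JNJ-56136379+NA.**

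| Assumption | Failure, at least | If no HBeAg loss |
|---|---|---|
| No HBsAg effect | 96.5% | 99.4% |
| Design effect, normal data | (12 × 0.436 + 48 × 0.491)/60 = 48% | (21 + 39 × 0.491)/60 = 67% |
| Design effect, skewed mixture | (12 × 0.698 + 48 × 0.811)/60 = 79% | (21 + 39 × 0.811)/60 = 88% |

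The mixture is my assumption. It has about 18% responders and reproduces the Table 7 mean and SD; the protocol says mixtures were simulated but gives no components. With 20%, 25% or 30% responders in the −0.05 subgroups, the pass probability is 0.206, 0.229 or 0.249, so failure is at least 75% to 79%.

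**Arm 1.** Protocol Section 1.3.4 reports 5 confirmed breakthroughs in 28 (18%), plus 2 unconfirmed (7/28 = 25%). Under the completed-weeks components essentially 28/28 are failures, unless someone had already met the Week 40/44 criteria. That leaves 23/28 (82%) failures without confirmed breakthrough, or 21/28 (75%) if the 2 unconfirmed are set aside as well. Week 4/8 non-response counts are not given.

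**Other non-virologic routes.** A safety concern fails the second bullet. A subject enrolled before Amendment 2 who declined the extension fails the third, through the 48-week component.

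**Date of failure.** SAP Section 7.1 lists sequencing time points for baseline, end of treatment, breakthrough, relapse and end of study, but none for failure. The second and third bullets supply no event date.

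**The case against.** Finite treatment is a stated study aim, and a composite that treats not reaching it as failure is a possible choice. Disposition tables (SAP Section 4.1) give the reasons for stopping study agent, so sponsor-stopped subjects remain identifiable. Both points are fair, but the label still conflicts with the SAP's other failure definitions and with how Section 7.3 uses it.

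Two stronger readings are tempting, and the documents do not support them.

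- A reader might infer that nearly everyone fails whatever the drug does, so the rule cannot separate JNJ-56136379 from NA. The rule does respond to an HBsAg effect: the active floor drops to 48% to 79% at the design effect, against about 96% in controls. It stays near the control rate only if HBsAg barely moves, as in the 28-day data in Protocol Section 1.1. Nor is any efficacy comparison harmed: the flag is absent from the SAP's secondary tabulations, compared proportions and time-to-event variables.
- A reader might infer that the resistance failure group becomes almost the whole trial. SAP Section 7.5 uses subjects with sequencing data as denominator, and sequencing depends on HBV DNA within the assay's limits. The range is not stated, but a control below LLOQ throughout is the subject least likely to contribute a sequence. Breakthrough also has its own sequencing time point and tables, so those counts are not diluted.

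The group taken from 5.3.1 may also draw on the other three failure definitions, so the Week 48 rule is one contributor. Sequenced subjects without breakthrough, such as those stopped in Arm 1, would still be counted.

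**Conclusion.** The point holds within limits. As written, the Week 48 flag labels as failures at least about 96% of placebo+NA controls, essentially all of Arm 1, and at least 48% to 79% of JNJ-56136379+NA subjects at the design effect. The primary endpoint and planned efficacy comparisons are untouched. What suffers is the set of treatment-failure resistance tables and the matching listing, where virologic failure is mixed with ineligibility to stop therapy and with administrative or safety stopping, and where the time of failure is undefined.

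The control figure rests on Week 24 values standing in for Weeks 40/44, on normality, and on a single criterion. The active range depends on an unstated distribution. Baseline HBsAg and HBeAg-loss rates are not given, so the true active rate cannot be determined. The Arm 1 statement follows from the completed-weeks wording, except for anyone who had already met the criteria.

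**What to change.** In the SAP Section 5.3 definitions, and for subject selection in Section 7.3 and the repeated text in Section 7.5:

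- Limit on-treatment failure in the Week 48 period to virologic events the SAP already defines: confirmed breakthrough on study treatment in any arm, and the Week 4/8 non-response carried over from the Week 24 definition.
- Set the time of failure to the first qualifying visit and add it to the time points in Section 7.1.
- Report not meeting the extension criteria as a separate non-failure category with its reason (HBV DNA, safety, consent, sponsor stop). Week 20 HBV DNA of 200 IU/mL or more should not itself count as failure: the protocol's Amendment 4 rationale recognises subjects with a pronounced decline who are not yet suppressed at Week 20.
- Report not meeting the completion criteria as another non-failure category. Keep the derivation, because this is the only place where the SAP spells out the components, and add a tabulation of the protocol's extension-phase endpoint.
- Reconcile the HBsAg threshold, which is below 500 IU/mL in the SAP and at or below 500 IU/mL in Protocol Section 6.3.

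The cost is a recoded flag, a date variable and slightly more SAP text. The data are already collected and no patient's management changes. The downside is a smaller reported failure count.

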**Table 4: response categories for viral activity parameters**

	Category criteria	Additional info
HBsAg Response	Subject who has achieved a HbsAg level <1000 IU/mL per time point	These proportions will also be included per analysis phase and analysis period. A subject will be included in the numerator if the response category is at least once met within the analysis phase/period.
	Subject who has achieved a HbsAg level <100 IU/mL per time point	
	Subject who has achieved a HbsAg level <10 IU/mL per time point	
	Subject who has achieved a HbsAg level <0.05 IU/mL per time point	
HBV DNA Response	Subject who has achieved a HBV DNA level <1 log10 IU/mL per time point	These proportions will also be included per analysis phase and analysis period. A subject will be included in the numerator if the response category is at least once met within the analysis phase/period.
	Subject who has achieved a HBV DNA level <2 log10 IU/mL per time point	
	Subject who has achieved a HBV DNA level <3 log10 IU/mL per time point	
	Subject who has achieved a HBV DNA level <20 IU/mL per time point	
	Subject who has achieved a HBV DNA level <60 IU/mL per time point	
	Subject who has achieved a HBV DNA level <100 IU/mL per time point	
	Subject who has achieved a HBV DNA level <1000 IU/mL per time point	
	Subject who has achieved a HBV DNA level <2000 IU/mL per time point	
	Subject who has achieved a HBV DNA level <20000 IU/mL per time point	
	Subject who has achieved a HBV DNA level < LLQ for target detected and not detected per time point	
	Subject who has achieved a HBV DNA level < LLQ for target not detected per time point	
	Subject who has achieved a HBV DNA level < LLQ for target detected per time point	
HBV RNA Response	Subject who has achieved a HBV RNA level <100 cp/mL per time point	These proportions will also be included per analysis phase and analysis period. A subject will be included in the numerator if the response category is at least once met within the analysis phase/period.
	Subject who has achieved a HBV RNA level <1000 cp/mL per time point	
	Subject who has achieved a HBV RNA level <2000 cp/mL per time point	
	Subject who has achieved a HBV RNA level <20000 cp/mL per time point	
	Subject who has achieved HBV RNA target not detected per time point	
	Subject who has achieved HBV RNA < LLOQ per time point	
	Subject who has achieved a HBV RNA level <250 cp/mL at week 24	
HbcrAg Response	Subject who has achieved a HBV DNA level <2 log10 IU/mL per time point	These proportions will also be included per analysis phase and analysis period. A subject will be included in the numerator if the response category is at least once met within the analysis phase/period.
	Subject who has achieved a HBV DNA level <3 log10 IU/mL per time point	
	Subject who has achieved a HBV DNA level $\geq 2 - < 3$ log10 IU/mL per time point	
HbsAg Reduction	Subject who has HbsAg reduced by > 0.3 log10 IU/mL from baseline per time point	These proportions will also be included per analysis phase and analysis period. A subject will be included in the numerator if the response category is at least once met within the analysis phase/period.
	Subject who has HbsAg reduced by > 0.5 log10 IU/mL from baseline per time point	
	Subject who has HbsAg reduced by > 1 log10 IU/mL from baseline per time point	
	Subject who has HbsAg reduced by > 2 log10 IU/mL from baseline per time point	
	Subject who has HbsAg reduced by > 3 log10 IU/mL from baseline per time point	
HbeAg Reduction	Subject who has HbeAg reduced by > 0.5 log10 IU/mL from baseline per time point	These proportions will also be included per analysis phase and analysis period. A subject will be included in the numerator if the response category is at least once met within the analysis phase/period.
	Subject who has HbeAg reduced by > 1 log10 IU/mL from baseline per time point	
	Subject who has HbeAg reduced by > 2 log10 IU/mL from baseline per time point	
HBV DNA Reduction	Subject who has HBV DNA reduced by > 1 log10 IU/mL from baseline per time point	These proportions will also be included per analysis phase and analysis period.

	Subject who has HBV DNA reduced by $> 2 \log_{10}$ IU/mL from baseline per time point	A subject will be included in the numerator if the response category is at least once met within the analysis phase/period.
	Subject who has HBV DNA reduced by $> 3 \log_{10}$ IU/mL from baseline per time point	
	Subject who has HBV DNA reduced by $> 1 \log_{10}$ IU/mL from baseline at week 4 and confirmation at week 8.	
HBV RNA Reduction	Subject who has HBV RNA reduced by $> 1 \log_{10}$ cp/mL from baseline per time point	These proportions will also be included per analysis phase and analysis period. A subject will be included in the numerator if the response category is at least once met within the analysis phase/period.
	Subject who has HBV RNA reduced by $> 2 \log_{10}$ cp/mL from baseline per time point	
	Subject who has HBV RNA reduced by $> 3 \log_{10}$ cp/mL from baseline per time point	
HbcrAg Reduction	Subject who has HBV DNA reduced by $> 0.5 \log_{10}$ IU/mL from baseline	These proportions will also be included per analysis phase and analysis period. A subject will be included in the numerator if the response category is at least once met within the analysis phase/period.

